4.1 Analysis Conventions

This section details general conventions to be used for the statistical analyses. Departures from these general conventions may be given in the specific detailed sections of this analysis plan. All data were collected using electronic case report forms (eCRFs).

- For all analyses, each dose level and overall will be summarized using descriptive summary statistics. Each treatment group will have a cohort number and data will be summarized in all tables, listings, and figures by treatment or cohort number. No statistical comparison of dose levels will be performed.
- Summary statistics will consist of the number and percentage for categorical variables, and the number of observations (n), mean, standard deviation (Sd), minimum, median, and maximum values for continuous variables. When the standard deviation cannot be calculated, a hyphen (-) will be used.
- All mean and median values will be formatted to one more decimal place than the
 measured value on the eCRF. Standard deviation values will be formatted to two more
 decimal places than the measured value on the eCRF. Minimum and maximum values
 will be presented with the same number of decimal places as the measured value on the
 eCRF.
- The number and percentages will be presented in the form XX (XX) where the percentage is in the parentheses. Unless otherwise specified, the denominator for percentages will be the number of patients in a given dose level within the analysis population of interest.
- All summary tables will include the analysis set sample size (i.e., number of patients).
- Baseline is defined as the last planned assessment before the first administration of study drug, unless otherwise specified. Typically this will be the Cycle 1 Day.
- Change from baseline will be calculated as follows:

Change from baseline = Post-baseline value – baseline value.

- Age will be calculated as the integer: (Date of informed consent date of birth)/365.25, rounded down to the nearest integer.
- Duration of time on study drug (days) = Date of last injection date of first injection+1.
- Date and time variables will be formatted as DDMMMYYYY hh:mm for presentation.

TPBS001 Version 6 (based on TPQA036 Version 2)

CONFIDENTIAL

| Sponsor: | Almac | Protocol Number: | ALM201/0001 |
|----------|-------|------------------|-------------|
| | | | |

- Summary tables with present data from scheduled assessments; listings will include all data, sorted by date.

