Lab values will be expressed in SI units. Any lab data collected from local labs that are nont in SI units will be converted in the analysis dataset to SI units prior to summarization. Actual and change from baseline summary statistics will be presented at each scheduled time point of the study for each lab parameter. Laboratory parameters with categorical results will be summarized with the number and percentage of patients. Repeat and unscheduled measurements will not be summarized; however, they will be in the data listings.

Shift tables from baseline result to worst post-baseline result will be generated. In the shift tables, results will be categorized as low, normal, high, including low clinically significant and high clinically significant when available. If a patient has both low and high post-baseline values, the summary table will display the result with the greatest absolute departure from the normal limits for that parameter. The denominators for the percentages will be the number of patients with non-missing data at both the baseline and any post-baseline time point for a parameter.

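### The laboratory shift tables promise each patient's worst value, but two SAP rules can keep that value out of the table

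*SAP*

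**What the plan says.** SAP 4.7.2 (Laboratory Measurements) sets the aim: "Shift tables from baseline result to worst post-baseline result will be generated". It also sets the cells: "In the shift tables, results will be categorized as low, normal, high, including low clinically significant and high clinically significant when available".

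For a patient with values on both sides of the range, one result is chosen: "the summary table will display the result with the greatest absolute departure from the normal limits for that parameter".

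On extra tests, the same section says: "Repeat and unscheduled measurements will not be summarized; however, they will be in the data listings". The general convention in SAP 4.1 agrees: "Summary tables with present data from scheduled assessments; listings will include all data, sorted by date". SAP 4.1 allows exceptions ("Departures from these general conventions may be given in the specific detailed sections of this analysis plan"), but 4.7.2 gives none for the shift tables.

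The percentages in the shift tables are based on "the number of patients with non-missing data at both the baseline and any post-baseline time point for a parameter". Separately, "Actual and change from baseline summary statistics will be presented at each scheduled time point of the study for each lab parameter".

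**The concern.** Safety and tolerability is the primary objective, and a worst-value shift table is where a reader looks for the most serious laboratory change in each patient. The plan sets up cells for clinically significant lows and highs, then selects the displayed result without using that information. It also leaves out the tests done between scheduled visits. The general footnotes to the schedule in SAP 3.3 allow additional assessments when clinically indicated, and those are occasions on which an extreme value may well be found.

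If either rule takes effect, the table reports a milder or different abnormality than the patient had, under a label that says otherwise.

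**Working it through.** The plan states no figure to reproduce. The check applies the SAP rule as written.

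**1. Choosing between a low and a high**

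Let x be the low value and y the high value.

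- Low departure = LLN − x
- High departure = y − ULN
- The high is displayed when y − ULN > LLN − x, that is, when y > ULN + LLN − x.

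*Without any reference range.* Take a low flagged clinically significant, with departure d. Any high with departure greater than d displaces it, whether or not the high is flagged. The significance category plays no part in the selection.

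*Bound for an analyte that cannot be negative.* Since x ≥ 0, the low departure is at most LLN, while the high departure has no such cap. Any y above ULN + LLN therefore hides every possible low, including zero.

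*Illustration.* The documents give no reference ranges, so those below are assumptions.

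- Neutrophils 2.0-7.5: a low of 0.4 departs by 2.0 − 0.4 = 1.6, and a high of 9.5 departs by 9.5 − 7.5 = 2.0. The high is shown. A value of zero is hidden by any high above 7.5 + 2.0 = 9.5, which is 1.27 × ULN.
- Varying the neutrophil range, a low of 0.4 is displaced by a high above:
  - 7.0 + 1.5 − 0.4 = 8.1 (range 1.5-7.0)
  - 7.5 + 1.8 − 0.4 = 8.9 (range 1.8-7.5)
  - 8.0 + 2.0 − 0.4 = 9.6 (range 2.0-8.0)
  
  These are 1.16 to 1.20 × ULN.
- Platelets 150-400: a low of 20 is displaced by a high above 400 + 150 − 20 = 530, about 1.3 × ULN.
- Potassium 3.5-5.3 and sodium 133-146: ULN + LLN is 8.8 and 279, so complete hiding is not realistic for these two.

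**2. Unscheduled values**

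The texts fit together as follows.

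- SAP 4.1 limits summary tables to scheduled assessments.
- SAP 4.7.2 says repeat and unscheduled laboratory values are listed and not summarised.
- The sentence in 4.7.2 on patients with both lows and highs itself calls the shift table a summary table.
- No departure is stated for the shift tables.

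As written, then, unscheduled values are excluded from the shift tables. This matters more as scheduled testing thins out. From Cycle 9, the SAP 3.3 schedule places chemistry and haematology on Day 1 of each cycle and at the Final Study Visit, so a test in between is unscheduled.

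**3. Comparison with other worst-value outputs in the SAP**

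AE tables by maximum grade (SAP 4.7.1) take the highest grade. The ECG shift (SAP 4.7.5) takes the worst interpretation on a scale of normal, abnormal not clinically significant and abnormal clinically significant. The laboratory shift is the one that ranks by raw distance.

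**4. Size if it happens**

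The protocol synopsis describes cohorts of 1, 3 or up to 6 patients. One patient in the wrong cell moves a cohort percentage by 1/1 = 100, 1/3 = 33.3 or 1/6 = 16.7 points. That is true of any table in cohorts this small. It shows only that a single case would be visible, and says nothing about how often one occurs.

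**The case against.** The strongest reply is that the rule is pre-specified and deterministic, and that other outputs largely cover the gap. Every value is listed. Abnormalities reported as adverse events reach the tables by CTCAE grade and those for Grade 3 or above. The by-visit statistics include the minimum and maximum, and in a one-patient cohort the minimum is that patient's own value. Most of this stands and keeps the point small. However, the by-visit statistics use scheduled values only and show neither the significance category nor the patient's shift from baseline.

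The significance argument also depends on flags that the SAP uses only where available. That stands too. Where there are no flags, what remains is the ULN + LLN bound.

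Two stronger readings are tempting, and the documents support neither.

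- **That the SAP leaves open whether unscheduled values count.** A reader might infer this because the exclusion sentence ends the paragraph on by-visit summaries and the denominator refers to any post-baseline time point. But the exclusion is explicit in both 4.1 and 4.7.2, the shift table is itself called a summary table, and the denominator settles who is counted, not which values are eligible. The point is the consequence of a stated exclusion.
- **That the rule picks the less serious result at some calculable rate.** Such a rate needs a definition of severity, and the documents give none. Measuring distance in SD units on a log scale would make lows look under-ranked. On the original scale, dividing both departures by the same SD leaves their order unchanged, so the absence of scaling is not a defect in itself. The share of patients with both a low and a high would likewise have to be assumed.

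**Conclusion.** The point holds as a minor one. Two stated rules can keep a patient's worst result out of a table that promises it: selection by distance without regard to clinical significance, and the exclusion of repeat and unscheduled values.

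The displacement of a significant low by a non-significant high follows from the SAP's wording alone, given that flags exist. The ULN + LLN bound needs only that the analyte cannot be negative. The numerical thresholds rest on assumed reference ranges.

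Only patients abnormal in both directions on the same parameter, or whose worst value was unscheduled, are affected. The documents do not allow either group to be counted, and the first may be close to empty. No dose or DLT decision rests on these tables: escalation decisions belong to the Cohort Review Committee during the study, and this SAP describes the final analysis of Part 1.

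**What to change.** In SAP 4.7.2:

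1. Replace the single shift with two per parameter, baseline to lowest and baseline to highest post-baseline value. A patient with both then appears in both, and no rule for choosing is needed.
2. State that all post-baseline values, including repeat and unscheduled ones, enter the shift tables, as an exception to SAP 4.1. Keep the by-visit actual and change-from-baseline summaries on scheduled values only.
3. If one shift per patient is kept, rank clinically significant results above non-significant ones where flags are available, and compare distance only within the same rank.

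The cost is a few sentences of SAP text and minor programming on data already collected and listed. The downside is slightly longer tables.

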4.7.3 Physical Examinations and Pregnancy Tests

All PE results will be presented in data listings. No pregnancy testing was conducted during this study.

4.7.4 Eastern Clinical Oncology Group Performance Status (ECOG PS)

Frequencies and percentage of patients with each ECOG performance status (PS) will be summarized as a categorical variable by cycle and worst status overall. All ECOG PS will be presented in a data listing.

4.7.5 12-Lead Electrocardiogram

The actual ECG measurements at each study evaluation time point along with the corresponding change from baseline calculation will be summarized for heart rate, PR, QRS, QT and QTc calculated using Fridericia's correction.

Overall ECG interpretations will be summarized using a shift table from baseline to the worst post-baseline interpretation. ECG interpretations will be reported as normal, Abnormal Not Clinically Significant (NCS), or Abnormal Clinically Significant (CS).

The denominators for the percentages will be the number of patients with non-missing data at both the baseline and any post-baseline visit. Additionally, the number and percentage of patients with elevated QT interval corrected for Fridericia's formula (QTcF) (> 450 and > 470) will be summarized by visit.

All 12-Lead ECG data will be presented in a data listing.

4.7.6 Vital Signs

TPBS001 Version 6 CONFIDENTIAL Effective Date: 15th March 2017 (based on TPQA036 Version 2) Prior Effective Date: 9th October 2016

| Sı | ponsor: | Almac | Protocol Number: | ALM201/0001 |
|----|---------|-------|------------------|-------------|
| | | | | |

The actual vital signs measurements at each scheduled time point along with the corresponding change from baseline calculations will be summarized for systolic/diastolic blood pressure (mmHg), pulse (beats/min), temperature (°C), respiratory rate (breaths/min), and weight (kg).

All vital signs will be presented in a data listing.

4.7.7 Echocardiogram

Listings of the left ventricular ejection fraction (LVEF) obtained by echocardiogram or MUGA, at screening, will be presented in listings.

4.7.8 Immunogenicity and Pharmacodynamic Samples

Listings of all samples collected to assess biomarker and PharmD activity will be presented.

- Ascites Samples
- Blood Samples for Biomarkers
- Biopsy Samples Biomarkers
- Immunogenicity Samples
- Serum Tumour Marker Samples

CONFIDENTIAL

5 Tables and Listings

5.1 Table Format

All output will be produced using SAS version 9.1.3 or a later version.

In the top left portion of each table/listing, a *table/listing number* followed by the *title* of the table/listing will be presented. After the title line, optional *sub-title* or *population* information can be presented. Horizontal lines will appear before and after the column heading of the table/listing. *Footnotes* will be put under the main body of text at the bottom of the page.

The *sponsor name*, *protocol number*, programmers User ID, status of the table/listing (i.e. draft or final) and *SAS program name* will appear bottom left in a string and the *page number* will appear on the bottom right corner of each table/listing. The *date and time of creation* of table/listing will appear bottom left under the sponsor name. The source listing number will appear bottom left.

A *landscape layout* is proposed for both table and listing presentations.

The *left* and *right margins* of all tables and listings will be a minimum of 2.1 cm from the left and 1.9cm from the right. The *top and bottom margins* will be a minimum 2.92cm. *Header and footer* will be both 1.27 cm.

There is no special requirement of *font type* and *size*, but an *8-point* font size for tables and *7*or *8-point* for listings is proposed using *Courier New* font. A maximum SAS line size=141 and page size=44 for *8-point* font size, and line size=161 and page size=50 for *7-point* will be used so as to fit on both UK and US paper sizes.

In a listing, in the case that a patient's record has been continued to the next page, an appropriate identification (e.g., the patient ID number) must be presented at the beginning of that page.

5.2 Conventions

Unless otherwise specified, in summary tables of continuous variables, the minimum and maximum values will be displayed to the same number of decimal places as the raw data, the mean and median will be presented to one extra decimal place compared to the raw data, and the standard deviation will be displayed to two extra decimal places compared to the raw data. Wherever possible, data will be decimal aligned.

Unless otherwise specified frequency tabulations will be presented by number and percentage, where the percentage is presented in brackets to 1 decimal place.

Any date information in the listing will use the *date9*. format, for example, 07MAY2002. In the listing, a unit associated with a variable will be presented only once within parentheses either below or next to that variable in the heading portion. If a parameter has multiple units, each unit will be displayed only once, as applicable.

All tables will have their source listing referenced in a footnote. Listings should be sorted by treatment group, patient and visit and have the source data received by data management referenced in a footnote. All tables and listings will be converted into Microsoft Word documents and collated into two complete documents.

TPBS001 Version 6 (based on TPQA036 Version 2)

CONFIDENTIAL

6 References

Hinnen P and Eskens F A L M. (2007) Vascular disrupting agents in clinical development. Br J Cancer. Apr 23, 96(8): 1159–1165.

Eskander RN and Tewari KS (2014) Incorporation of anti-angiogenesis therapy in the management of advanced ovarian carcinoma – Mechanistics, review of phase III randomized clinical trials, and regulatory implications Gynecologic Oncology 132: 496-505

